**Study Title**

Percutaneous Deep Vein Arterialization for the Treatment of  
Late-Stage Chronic Limb-Threatening Ischemia (The PROMISE  
II Trial)

**Investigational Device**

LimFlow System™

**Indication for Use**

The LimFlow System is indicated to treat chronic limb-  
threatening ischemia by creating an arteriovenous (AV)  
connection in the below-the-knee vasculature for treatment of  
chronic limb-threatening ischemia (CLTI).

**Intended Use**

The LimFlow System is intended for endovascular, minimally  
invasive procedures in patients who have a clinical diagnosis of  
chronic limb-threatening ischemia and who have been  
determined to have no surgical or endovascular treatment option  
(i.e., “no option”).

**Study Objective**

The objective of this US pivotal trial is to investigate the safety  
and effectiveness of the LimFlow System for creating an AV  
connection in the Below The Knee (BTK) vascular system using

an endovascular, minimally invasive approach to arterialize the pedal veins for the treatment of chronic limb-threatening ischemia in subjects ineligible for conventional endovascular or surgical limb salvage procedures.

**Study Population**

The study population is comprised of subjects who are confirmed as “no option” (ineligible for conventional endovascular or surgical limb salvage procedures) by the Independent Review Committee (IRC). “No option” is defined as either a) absence of a usable pedal artery target (endovascular or surgical approach), or b) the presence of a pedal artery target with absence of a viable single-segment vein in either lower extremity or either arm that could be used for autogenous vein conduit.

**Study Design**

A prospective, single-arm, multi-center pivotal study designed to confirm the safety and effectiveness of the LimFlow System. The study will consist of a minimum of 60 and up to 120 subjects. This study utilizes a Bayesian Goldilocks adaptive design for sample size determination.

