#### 4.5 Number of Subjects

The study will enroll at least 60 and up to 120 subjects, based upon the planned adaptive trial design sample size re-estimation during enrollment.

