**11.3 Determination of Sample Size**

Although the analysis methods are Bayesian, the following frequentist scenarios are used to guide the determination of minimum and maximum sample size.

- According to PASS 13, when using  $\alpha = 0.025$  (one-sided) in an exact binomial test, achieving 90% power to test the hypotheses in Section 7.1 when the true AFS = 0.70 would require a sample size of 101 subjects. Allowing for 10% missing data would require a sample size of N=113 subjects
- If the true AFS = 0.68, a sample size of 101 subjects would achieve 81% power. Allowing for 10% missing data would require a sample size of N=113 subjects
- If the true AFS = 0.75, 90% power requires a sample size of N=56 subjects. Allowing for 10% missing data would require a sample size of N=63 subjects.

There is considerable uncertainty in the true AFS rate  $\phi$ . Consequently, it is desirable to utilize a study design that achieves at least 80% power when  $AFS \geq 0.68$  and 90% power when  $AFS \geq 0.70$ , while allowing early stopping of enrollment if the AFS rate proves to be very high (e.g., 0.75) or very low ( $\leq 0.54$ ). Therefore, the study design was selected wherein the sample size is adaptively determined, with a minimum value of 60 and a maximum value of 120.

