**Table 7 Operating Characteristics of the Design**

Expected Accrual Rate (5/mo)			Probability for Stopping Enrollment (by Reason)				
$\phi^*$	Power	Average N	At N=60 (Futile, Promise)	At N=75 (Futile, Promise)	At N=90 (Futile, Promise)	At N=105 (Futile, Promise)	At N=120 (Max)
0.54	0.0244	76.0	0.4647	0.2317	0.1379	0.0688	0.0810
			0.0019	0.0033	0.0049	0.0058	
0.65	0.6336	95.2	0.0529	0.0594	0.0594	0.0466	0.3166
			0.0911	0.1159	0.1287	0.1294	
0.66	0.7130	94.3	0.0355	0.0422	0.0478	0.0357	0.2967
			0.1181	0.1336	0.1475	0.1429	
0.67	0.7810	92.3	0.0260	0.0314	0.0374	0.0238	0.2614
			0.1486	0.1578	0.1654	0.1482	
0.68	0.8423	90.3	0.0208	0.0228	0.0235	0.0180	0.2222
			0.1726	0.1865	0.1786	0.1550	
0.69	0.8879	87.9	0.0112	0.0158	0.0171	0.0118	0.1890
			0.2190	0.2049	0.1783	0.1529	
0.70	0.9253	84.6	0.0093	0.0099	0.0133	0.0080	0.1384
			0.2654	0.2287	0.1846	0.1424	
0.75	0.9945	71.7	0.0005	0.0004	0.0011	0.0001	0.0227
			0.5219	0.2699	0.1316	0.0518	

In Table 7, the type I error rate (when  $\phi^* = 0.54$ ) is 0.0244, and the average achieved sample size is 76.0. In this scenario,

- the trial stopped accruing at N=60 46.66% of the time (46.47% for futility, 0.19% for promising trend),
- at N=75 23.50% of the time (23.17% for futility, 0.33% for promising trend),
- at N=90 14.28% of the time (13.79% for futility, 0.49% for promising trend),
- at N=105 7.46% of the time (6.88% for futility, 0.58% for promising trend, and
- at N=120 8.10% of the time.

When  $\phi^* = 0.70$ , the estimated power is 0.9253, and the average achieved sample size is 84.6. In this scenario, the trial stopped accruing at N=60 27.47% of the time (0.93% for futility, 26.54% for promising trend), at N=75 23.86% of the time (0.99% for futility, 22.87% for promising trend), at N=90 19.79% of the time (1.33% for futility, 18.46% for promising trend), at N=105 15.04% of the time (0.80% for futility, 14.24% for promising trend), and at N=120 13.84% of the time. Overall, the design performs as intended, with type I error rate  $\leq 0.025$ , high power when  $\phi^* \geq 0.68$ , and smaller sample sizes when the simulated amputation-free survival rate  $\phi$  is particularly high (e.g.,  $\phi^* = 0.75$ ) or particularly low (e.g.,  $\phi^* = 0.54$ ).

Simulation details and sensitivity of the operating characteristics to assumptions made about the data mechanism can found in the SAP for the study.

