A prospective, single-arm, multi-center pivotal study designed to confirm the safety and effectiveness of The LimFlow System. The study will consist of a minimum of 60 and up to 105 subjects. This study utilizes a Bayesian Goldilocks adaptive design for sample size determination.

Number of Sites

Up to 25 sites in the United States, United Kingdom, and Japan

Primary Endpoint

Amputation Free Survival (AFS) defined as freedom from major amputation or death at 6 months, compared to a literature-based performance goal.

Major Amputation: above-ankle amputation of the index limb or

Death: all-cause mortality

Secondary Endpoints

Primary Patency: Defined as the absence of occlusion of the endovascular intervention maintained with no additional or secondary surgical or endovascular procedures, at 30 days and 6 months.

Primary Assisted Patency: Defined as the absence of occlusion of the endovascular intervention maintained with the use of additional or secondary surgical or endovascular procedures, as long as occlusion of the primary treated site has not occurred, at 30 days and 6 months.

Secondary Patency: Defined as the absence of occlusion of the endovascular intervention that is maintained with the use of additional or secondary surgical or endovascular procedures after occlusion occurs, at 30 days and 6 months.

Limb Salvage: Defined as the percentage of subjects with freedom from above-ankle amputation of the index limb, evaluated at 30 days, 3 and 6 months.

Change in Rutherford Classification: Defined as a change of one

STATISTICAL ANALYSIS PLAN

class or greater, as evaluated at 30 days, 3 and 6 months.

Technical Success: Defined as the successful creation of an arteriovenous fistula in the desired limb location with immediate morphological success.

Procedural Success: Defined as the combination of technical success, and absence of all-cause death, above-ankle amputation or clinically driven major re-intervention¹ of the stent-graft at 30 days.

Target Wound Healing: Defined as complete healing of the patient's target wound as evaluated at 30 days, 3, 6, 9 months, and 1 year.

All Wound Healing: Defined as complete healing of the patient's wounds as evaluated at 30 days, 3, 6, 9 months, and 1 year.

All Wound Area Reduction: Defined as reduction in area of the patient's wounds as evaluated at 30 days, 3, 6, 9 months, and 1 year.

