			0.2190	0.2049	0.1783	
0.70	0.9051	82.5	0.0093	0.0099	0.0133	0.2888
			0.2654	0.2287	0.1846	
0.75	0.9915	71.4	0.0005	0.0004	0.0011	0.0746
			0.5219	0.2699	0.1316	

In Table 2, the observed type I error rate (when $\phi^* = 0.54$) is 0.0239 and the average achieved sample size is 74.8. In this scenario, the trial stopped accruing at N=60 46.66% of the time (46.47% for futility, 0.19% for promising trend), at N=75 23.50% of the time (23.17% for futility, 0.33% for promising trend), at N=90 14.28% of the time (13.79% for futility, 0.49% for promising trend), and at N=105 15.56% of the time.

When $\phi^* = 0.70$, the estimated power is 0.9051 and the average achieved sample size is 82.5. In this scenario, the trial stopped accruing at N=60 27.47% of the time (0.93% for futility, 26.54% for promising trend), at N=75 23.86% of the time (0.99% for futility, 22.87% for promising trend), at N=90 19.79% of the time (1.33% for futility, 18.46% for promising trend), and at N=105 28.88% of the time. Overall, the design performs as intended, with type I error rate ≤ 0.025 , high power when $\phi^* \geq 0.68$, and smaller sample sizes when the simulated amputation-free survival rate ϕ is particularly high (e.g., $\phi^* = 0.75$) or particularly low (e.g., $\phi^* = 0.54$).

STATISTICAL ANALYSIS PLAN

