6.6.1 Comparison to Operating Characteristics of Original Design

Table 3 displays operating characteristics of the original design (with a maximum of N=120 subjects). In comparing Table 2 and Table 3, it is clear that the stopping probabilities at N=60, 75, and 90 have not changed, and the probability of stopping at N=105 in Table 2 is the sum of the probabilities of stopping at N=105 and N=120 in Table 3. For example, in the $\phi^* = 0.54$ row, Table 2 shows a probability = 0.1556 of stopping enrollment at N=105, which is the sum of 0.0688 + 0.0058 + 0.0810 (entries in the N=105 and N=120 columns in Table 3). The Average N in Table 3 tends to be slightly smaller, as is the Power. The observed Type I error rate of 0.0239 remains < 0.025 and not meaningfully different from the value 0.0244 seen in Table 3.

Table 3 Operating Characteristics of the Original Design

Expected Accrual Rate (5/mo)			Probability for Stopping Enrollment (by Reason)				
ϕ^*	Power	Average N	At N=60 (Futile, Promise)	At N=75 (Futile, Promise)	At N=90 (Futile, Promise)	At N=105 (Futile, Promise)	At N=120 (Max)
0.54	0.0244	76.0	0.4647	0.2317	0.1379	0.0688	0.0810
			0.0019	0.0033	0.0049	0.0058	
0.65	0.6336	95.2	0.0529	0.0594	0.0594	0.0466	0.3166
			0.0911	0.1159	0.1287	0.1294	
0.66	0.7130	94.3	0.0355	0.0422	0.0478	0.0357	0.2967
			0.1181	0.1336	0.1475	0.1429	
0.67	0.7810	92.3	0.0260	0.0314	0.0374	0.0238	0.2614
			0.1486	0.1578	0.1654	0.1482	
0.68	0.8423	90.3	0.0208	0.0228	0.0235	0.0180	0.2222
			0.1726	0.1865	0.1786	0.1550	
0.69	0.8879	87.9	0.0112	0.0158	0.0171	0.0118	0.1890
			0.2190	0.2049	0.1783	0.1529	
0.70	0.9253	84.6	0.0093	0.0099	0.0133	0.0080	0.1384
			0.2654	0.2287	0.1846	0.1424	
0.75	0.9945	71.7	0.0005	0.0004	0.0011	0.0001	0.0227
			0.5219	0.2699	0.1316	0.0518	

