6.7.1 Comparison to Operating Characteristics of Original Design

Table 5 displays corresponding operating characteristics of the original design (with a maximum of N=120 subjects). In comparing Table 4 and Table 5, it is clear that the stopping probabilities at N=60, 75, and 90 have not changed, and the probability of stopping at N=105 in Table 4 is the sum of the probabilities of stopping at N=105 and N=120 in Table 5. For example, in the first row, Table 4 shows a probability = 0.1403 of stopping enrollment at N=105, which is the sum of 0.0617 + 0.0061 + 0.0725 (entries in the N=105 and N=120 columns in Table 5). The Average N in Table 5 tends to be slightly smaller. The observed power (i.e. Type I error rate) is not meaningfully different (0.0260 and 0.0253 in Table 4, 0.0260 and 0.0246 in Table 5).

Table 5 Operating Characteristics of the Original Design with Varying Accrual Rates

ϕ^*	Power	Average N	Probability for Stopping Enrollment (by Reason)				
			At N=60 (Promise, Futile)	At N=75 (Promise, Futile)	At N=90 (Promise, Futile)	At N=105 (Promise, Futile)	At N=120 (Max)
Slower Accrual Rate (3/month) – Null Scenario							
0.54	0.0260	74.7	0.4978	0.2245	0.1241	0.0617	0.0725
			0.0044	0.0038	0.0051	0.0061	
Faster Accrual Rate (7/month) – Null Scenario							
0.54	0.0246	78.2	0.4020	0.2503	0.1543	0.0790	0.0956
			0.0038	0.0035	0.0051	0.0064	

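### The protocol still carries the 120-subject design and its power, and SAP 6.6.1 and 6.7.1 name the wrong table when describing the effect of the cut to 105

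*Protocol*

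**What the plan says.** **Protocol.** The synopsis states "The study will consist of a minimum of 60 and up to 120 subjects". Section 4.5 repeats it ("The study will enroll at least 60 and up to 120 subjects"), and section 11.3 settles on an adaptive sample size "with a minimum value of 60 and a maximum value of 120". Sections 4.1, 11, 11.1 and 11.5.2 and the COVID-19 rule use the same cap. Table 6 has four interim looks, the last at N=105 with thresholds 0.90 (promise) and 0.15 (futility). Table 7 gives power of 0.8423 at AFS 0.68. At AFS 0.70 its text says "the estimated power is 0.9253, and the average achieved sample size is 84.6".

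**SAP.** The section headed Protocol Synopsis states "The study will consist of a minimum of 60 and up to 105 subjects". Section 4 explains that the maximum was lowered after the N=90 assessment and before the N=105 one, for practical and commercial reasons, and points to sections 6.6 and 6.7 for the statistical effect. Table 1 drops the fourth look. Section 6.4 deliberately keeps PPfut defined at N=120. Table 2 (revised design) gives power of 0.8019 at AFS 0.68. At 0.70 the text says "the estimated power is 0.9051 and the average achieved sample size is 82.5".

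SAP 6.6.1 introduces Table 3 as the original 120-subject design and then says: "The Average N in Table 3 tends to be slightly smaller, as is the Power". SAP 6.7.1 introduces Table 5 as the original design under other accrual rates and says: "The Average N in Table 5 tends to be slightly smaller".

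**The concern.** Two problems meet here. First, the protocol and the SAP give different maxima, different numbers of looks and different power for one trial, and neither says which governs. Someone working from the protocol would take the trial to have a look at N=105, possible continuation to 120, and about 84% and 93% power at the two planning values.

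Second, a cut to the maximum after three interim assessments needs a correct account of what it cost. Section 4 sends the reader to 6.6 and 6.7 for that account. Taken literally, the sentence in 6.6.1 says the original design had less power, so that the cut raised it. The tables on either side of the sentence show the opposite.

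**Working it through.** **Inputs.** Power, average N and stopping probabilities are from SAP Tables 2 to 5; protocol Table 7 is identical to SAP Table 3. The aims, at least 80% power at AFS 0.68 and 90% at 0.70, are in protocol 11.3 and SAP 6.3. Each table row rests on 10,000 simulated trials (SAP 6.6 and 6.7).

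**Step 1: are the printed tables sound?** Average N = Σ N × Pr(stop at N).

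- AFS 0.68, looks 60 to 90: 60(0.0208+0.1726) + 75(0.0228+0.1865) + 90(0.0235+0.1786) = 11.604 + 15.698 + 18.189 = 45.491.
- Original: 45.491 + 105(0.0180+0.1550) + 120(0.2222) = 45.491 + 18.165 + 26.664 = 90.3, as printed.
- Revised: 45.491 + 105(0.3952) = 45.491 + 41.496 = 87.0, as printed. Also 0.0180 + 0.1550 + 0.2222 = 0.3952.

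All eight rows of Tables 2 and 3 reproduce in this way, and every N=105 probability in Table 2 equals the Table 3 sum. The tables are right; the sentence is what has to change.

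**Step 2: direction and size of the change.**

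| AFS | Avg N, original (Table 3) | Avg N, revised (Table 2) | Power, original | Power, revised | Change |
|---|---|---|---|---|---|
| 0.54 | 76.0 | 74.8 | 0.0244 | 0.0239 | −0.0005 |
| 0.65 | 95.2 | 90.4 | 0.6336 | 0.5892 | −0.0444 |
| 0.66 | 94.3 | 89.9 | 0.7130 | 0.6682 | −0.0448 |
| 0.67 | 92.3 | 88.4 | 0.7810 | 0.7419 | −0.0391 |
| 0.68 | 90.3 | 87.0 | 0.8423 | 0.8019 | −0.0404 |
| 0.69 | 87.9 | 85.1 | 0.8879 | 0.8547 | −0.0332 |
| 0.70 | 84.6 | 82.5 | 0.9253 | 0.9051 | −0.0202 |
| 0.75 | 71.7 | 71.4 | 0.9945 | 0.9915 | −0.0030 |

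Both quantities are larger in Table 3 in every row (at 0.54 the power column is the type I error). For average N it could not be otherwise: each trial that would have reached 120 now ends 15 subjects earlier, so the drop is 15 × Pr(reach 120). At AFS 0.68 that is 15 × 0.2222 = 3.3 = 90.3 − 87.0.

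**Step 3: SAP 6.7.1.** Average N is 73.6 (slower accrual) and 76.7 (faster) in Table 4 (revised), against 74.7 and 78.2 in Table 5 (original), so the sentence is again reversed. Type I error is 0.0260 and 0.0253 (revised) against 0.0260 and 0.0246 (original): equal in one row and slightly higher in the revised design in the other. The SAP reports these four values correctly.

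**Step 4: margin against the aims.**

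- AFS 0.68: the margin goes from 0.8423 − 0.80 = 0.0423 to 0.8019 − 0.80 = 0.0019. Monte Carlo SE = √(0.8019 × 0.1981 / 10,000) = 0.0040; approximate 95% interval 0.794 to 0.810.
- AFS 0.70: the margin goes from 0.0253 to 0.0051. SE = √(0.9051 × 0.0949 / 10,000) = 0.0029; approximate 95% interval 0.899 to 0.911.

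**Step 5: independent simulation.** This used the SAP 6.7 hazards scaled to each AFS, 10% uniform loss to follow-up, 5 per month accrual after the ramp-up, the Gamma imputation model, the Beta(1,1) prior, the 0.977 threshold and the documented stopping thresholds. It ran 20,000 trials per scenario with 1,000 predictive draws, both maxima on the same simulated trials.

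| AFS | Original: simulated (printed) | Revised: simulated (printed) | Simulated loss |
|---|---|---|---|
| 0.65 | 0.635 (0.6336) | 0.594 (0.5892) | 4.1 points |
| 0.68 | 0.839 (0.8423) | 0.802 (0.8019) | 3.7 points |
| 0.70 | 0.922 (0.9253) | 0.899 (0.9051) | 2.3 points |

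The printed losses at these values are 4.4, 4.0 and 2.0 points. Direction and size agree.

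**The case against.** The strongest reply is that nothing is hidden. SAP section 4 declares the revision, its timing and its reason. Tables 2 and 3 are printed in full under titles naming the revised and original designs. The worked example in 6.6.1 (0.0688 + 0.0058 + 0.0810 = 0.1556) is correct, and anyone who compares the two tables sees the loss. Protocol Table 7 is also right for the design the protocol describes. All of this stands. What remains is a protocol that does not match the revised design and a table reference that reverses a conclusion; no table entry is wrong.

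Some stronger readings are tempting, and the documents do not support them:

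- A reader might infer that the SAP conceals the cost of the cut. It prints that cost; only the sentences misdescribe it.
- A reader might infer that the revised design misses its power aims. Table 2 meets both (0.8019 and 0.9051). The simulated 0.899 at AFS 0.70 shows how thin the margin is, not a failure: the gap of 0.006 is within the combined simulation error of the two estimates.
- A reader might infer from the guide figure of 113 subjects (AFS 0.70, 10% missing data) that 105 is too few. That is a fixed-sample exact-binomial guide. The design's power comes from simulating the adaptive rule with 10% loss to follow-up.
- A reader might infer that 6.7.1 also misstates power. It covers only AFS 0.54, and its type I error comparison is correct.
- A reader might take 105 as a fixed size. It is a maximum, and stopping at 60, 75 or 90 remains part of the rule.

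**Conclusion.** The point holds as a consistency and wording correction. The protocol's maximum (120), its fourth look at N=105 and its power (0.8423 and 0.9253) are not those of the SAP's design (105, three looks, 0.8019 and 0.9051). SAP 6.6.1 reverses the comparison of average N and power, and SAP 6.7.1 reverses average N only. The loss of power is at most 4.5 points (AFS 0.66), 4.0 at 0.68 and 2.0 at 0.70. Both power aims are still met, with almost no margin.

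This assumes that the protocol supplied is the version in force alongside the revised SAP; neither document mentions a later one. The power figures rest on the SAP's own assumptions about hazards, accrual and 10% loss to follow-up. The point makes no claim about type I error: the simulation gave 0.0275 (original) and 0.0265 (revised) against the printed 0.0244 and 0.0239, and it was not designed to settle differences of that size. The success threshold and the final test are unchanged by the revision.

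**What to change.** 1. **Protocol.** Change the maximum to 105 and the interim looks to three in the synopsis, 4.1, 4.5, 11, 11.1, 11.3 and 11.5.2, and change the cap in the COVID-19 rule. Replace Tables 6 and 7 and their text with SAP Tables 1 and 2, so that stated power is 0.80 at AFS 0.68 and 0.905 at 0.70. Keep PPfut defined at N=120, as SAP 6.4 does. A blanket replacement of 120 by 105 in 11.5.2 would change the futility rule and create a new conflict with the SAP.
2. **SAP 6.6.1.** Say that average N and power are smaller in Table 2 (revised), by up to 4.5 points of power.
3. **SAP 6.7.1.** Say that average N is smaller in Table 4 (revised). Leave the type I error sentence as it is.

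The SAP's own power figures need no change. The cost is amendment wording, and the protocol's stated power becomes slightly less favourable. No further patients or analyses are needed.

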**Number of Sites**

Up to 25 sites in the United States, United Kingdom, and Japan

**Primary Endpoint**

Amputation Free Survival (AFS) defined as freedom from major amputation and death (defined below) at 6 months, compared to a historical performance goal.

**Major Amputation:** above-ankle amputation of the index limb *and*

**Death:** all-cause mortality

**Secondary Endpoints**

**Primary Patency:** Defined as absence of occlusion of the endovascular intervention that is maintained without the need for additional or secondary surgical or endovascular procedures, at 30 days and 6 months.

**Primary Assisted Patency:** Defined as absence of occlusion of the endovascular intervention maintained with the use of additional or secondary surgical or endovascular procedures, as long as occlusion of the primary treated site has not occurred, at 30 days and 6 months.

**Secondary Patency:** Defined as absence of occlusion of the endovascular intervention that is maintained with the use of additional or secondary surgical or endovascular procedures after occlusion occurs, at 30 days and 6 months.

**Limb Salvage:** Defined as percentage of subjects with freedom

from above-ankle amputation of the index limb, evaluated at 30 days, 3 and 6 months.

**Change in Rutherford Classification:** Defined as a change of one class or greater, as evaluated at 30 days, 3 and 6 months.

**Technical Success:** Defined as the successful creation of an arteriovenous fistula in the desired limb location with immediate morphological success.

**Procedural Success:** Defined as the combination of technical success, and absence of all-cause death, above-ankle amputation or clinically driven major re-intervention of the stent graft at 30 days.

**Target Wound Healing:** Defined as complete healing of the patient's target wound as evaluated at 30 days, 3, 6, 9 months, and 1 year.

**All Wound Healing:** Defined as complete healing of the patient's wounds as evaluated at 30 days, 3, 6, 9 months, and 1 year.

**All Wound Area Reduction:** Defined as reduction in area of the patient's wounds as evaluated at 30 days, 3, 6, 9 months, and 1 year.

**Freedom from Contrast-Induced Nephropathy:** Defined as subjects without acute (within 72 hours after intravenous contrast administration) impairment of renal function, measured as an absolute  $\geq 0.5$  mg/dL (44  $\mu\text{mol/L}$ ) increase compared to baseline SCr value that results in a value above the upper limit of the normal range.

**Procedure Time:** Defined as the time of the first puncture (venous or arterial) to when the last catheter is removed.

**Radiation Exposure:** Defined as patient radiation exposure (in milligray) during the procedure.

**Contrast Volume:** Defined as the total volume of contrast media (in milliliters) given during the procedure.

---

 The creation of a new surgical bypass, the use of thrombectomy or thrombolysis (i.e., procedures done in the setting of lost primary-assisted patency), or major surgical revision such as a jump graft or an interposition graft performed for occlusion of the stent graft.

